4.2. Scientific Rationale for Study Design

Dosing with duvelisib 25 mg BID has been shown to be efficacious in multiple Phase 1-3 studies including subjects with iNHL. Data from the pivotal Phase 3 CLL/SLL study (DUO) and Phase 2 FL study (DYNAMO) showed that most tumor responses occurred by the end of Cycle 4 of duvelisib 25 mg BID treatment, and the majority of DIs for toxicity occurred primarily after 4 cycles. The post-hoc analysis of the DUO study showed that response to duvelisib was improved or maintained in most subjects who had ≥ 1 DI for > 1 week (84%) or > 2 weeks (82%), then followed by ≥ 3 weeks on duvelisib. PFS was also similar between subjects with ≥ 1 DI and those without DI for > 1 week or > 2 weeks within the first 3 months of therapy (median PFS: > 1 week, 17.8 vs 16.3 months; > 2 weeks, 17.8 vs 16.3 months) ([Flinn 2019](#)). These data support the hypothesis that prespecified 2-week drug holidays used in this study would not impact efficacy. Based on these results, the VS-0145-229 study will examine the effects of prespecified 2-week dose holidays on tumor responses (i.e., is uninterrupted dosing required in early cycles to

achieve responses, or can comparable tumor responses be achieved starting with alternating 2-week periods of dosing and holidays?) and safety/tolerability (i.e., will the holidays reduce the frequency, severity, and/or duration of AEs, allowing subjects to stay on treatment longer?).

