### 3.1 Overall Study Design and Plan

This is a Phase 2, randomized, open-label, multicenter, international 2-arm study designed to evaluate the efficacy and safety of alternative dosing schedules of duvelisib treatment in subjects with R/R iNHL who have received at least 1 prior systemic therapy.

Subjects will be stratified by the number of prior therapies (1 or  $> 1$ ), bulky disease status (longest diameter of baseline lesion  $< 5$  cm or  $\geq 5$  cm) and time since last recurrence ( $\geq 24$  months or  $< 24$  months).

Subjects will be randomized to Arm 1 or Arm 2 in a 1:1 fashion.

- Arm 1: duvelisib 25 mg BID for one 10-week cycle followed by 25 mg BID on Weeks 3 and 4 of each subsequent 4-week cycles until disease progression, unacceptable toxicity, or withdrawal.
- Arm 2: duvelisib 25 mg BID on Weeks 1, 2, 5, 6, 9 and 10 of one 10-week cycle, then on Weeks 3 and 4 of each subsequent 4-week cycles until disease progression, unacceptable toxicity, or withdrawal (Figure 1).

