#### 4.11.2 Adverse Events

Adverse events will be coded using Medical Dictionary for Regulatory Activities (MedDRA) Version 22 or higher. The severity grade of the AE will be assessed by the Investigator according to the National Cancer Institute Common Terminology Criteria for Adverse Events (NCI-CTCAE, Version 5.0). If an AE is not included in the NCI-CTCAE Version 5.0, the severity grade of the AE will be assessed by the Investigator according to the study protocol.

A treatment-emergent adverse event (TEAE) is defined as any AE that emerges or worsens in the period from the first dose of duvelisib to 30 days after the last dose of duvelisib. The onset date of an AE will be compared to the first dose date and the last dose date plus 30 days (inclusive) to determine whether the AE is treatment-emergent or not. Refer to [Section 4.3.1.2](#) for the algorithm to determine whether an AE is treatment emergent if the onset date of an AE is completely or partially missing.

TEAEs will be summarized for each treatment arm by MedDRA SOC and PT, or PT only, or SOC only. For summary tables by SOC and PT, SOC will be sorted alphabetically, and PT will be sorted by decreasing frequency in Arm 1 within each SOC. For summary tables by PT only, PT will be sorted by decreasing frequency. For selected summaries (indicated in the list below), TEAEs will be summarized by SOC, high-level group term (HLGT) and PT, sorted by most frequently occurring SOC.

If multiple TEAEs of the same PT are reported for a subject, only the maximum grade observed for this PT will be included in summary of TEAEs by grade; the subject will be counted only once in the number of subjects for this PT and only once for the number of subjects for the SOC to which the PT is classified.

An overview TEAE summary table will be provided which will include the number of subjects with AEs in selected categories. In addition, TEAEs will be summarized for the following categories, and will be tabulated by SOC and PT, unless otherwise specified.

- TEAEs (all grades, all causalities)
- Treatment-related TEAEs (all grades)
- TEAEs by maximum grade (all causalities)

- Treatment-related TEAEs by maximum grade
- Grade 3 or higher TEAEs (all causalities)
- Grade 3 or higher treatment-related TEAEs
- Treatment-emergent SAEs (all causalities)
- TEAEs resulting in discontinuation of study drug (all causalities)
- TEAEs resulting in dose hold (all causalities)
- TEAEs resulting in dose reduction (all causalities)

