- TEAEs resulting in dose hold or reduction (all causalities)
- TEAEs resulting in any dose modification (dose hold, dose reduction and/or discontinuation)
- TEAEs occurring during the first 10 weeks of treatment
- Treatment-related TEAEs resulting in discontinuation of study drug
- TEAEs by resolution status (resolved/resolved with sequelae vs. not resolved)
- Grade 3 and or higher TEAEs by resolution status (resolved/resolved with sequelae vs. not resolved)
- Treatment-emergent SAEs by resolution status (resolved/resolved with sequelae vs. not resolved)
- TEAEs resulting in death (all causalities)
- Treatment-related TEAEs resulting in death
- TEAEs reported in  $\geq 20\%$  of all treated subjects by PT (all grades, all causalities)
- Grade 3 or higher treatment-emergent AEs reported in  $\geq 20\%$  of all treated subjects by PT (all causalities)
- Treatment-emergent SAEs reported in  $\geq 2\%$  of all treated subjects by PT (all causalities)
- TEAEs reported in  $\geq 5\%$  of subjects and occurred at  $\geq 2\%$  higher incidence in subjects on Arm 1 (all grades, all causalities)
- Grade 3 or higher TEAEs reported in  $\geq 5\%$  of subjects on either arm (all causalities)

A by-subject listing of the following AE categories will be presented.

- All AEs (TEAEs will be flagged)
- All SAEs (TEAEs will be flagged)
- All SAE reported with the term disease progression
- TEAEs resulting in dose hold
- TEAEs resulting in dose reduction
- TEAEs resulting in discontinuation of study drug
- TEAEs resulting in death (see [Section 4.11.3](#) for full characterization of deaths)
- TEAEs resolved or resolved with sequelae
- TEAEs not resolved

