#### 4.11.2.1 Other Adverse Events of Interest

Selected MedDRA PTs will be combined to create grouped PTs or categories to further characterize risks associated with duvelisib. The following risks will be summarized as Adverse Event of Special Interest:

- Diarrhea/colitis
- Infections
  - All infections, excluding Pneumonia and COVID-19 infections
  - Pneumonia
  - COVID-19 infections
- Cutaneous reactions
- Non-infectious pneumonitis
- Neutropenia
- Hepatotoxicity (as defined by transaminase elevations)

The specific PTs that will be combined for each risk are defined in [Appendix 1](#).

For each risk, PTs will be summarized at the grouped PT and individual PT (and grouped SOC if applicable), at the subject level:

- TEAEs (all grades, all causalities)
- Treatment-related TEAEs (all grades)
- Grade 1 or 2 only TEAEs (all causalities)
- Grade 3 or higher TEAEs (all causalities)
- Treatment-emergent SAEs (all causalities)
- TEAEs resulting in dose holds
- TEAEs resulting in dose reductions
- TEAEs resulting in dose holds or reductions
- TEAEs resulting in discontinuation of study drug (all causalities)
- Time to initial onset (defined as AE start date – first dose date + 1)

In addition, the following summaries will be created for each grouped PT within each grouped SOC, at the event level:

- Summary of dose modifications
  - Number of events resulting in dose holds
  - Number of events resulting in dose reductions
  - Number of events resulting in dose holds or reductions
  - Number of events resulting in discontinuation of study drug
- Summary of outcome
  - Number of events resolved
  - Number of events resolved with sequelae
  - Number of events resolved or resolved with sequelae
  - Number of events not resolved
- Duration of AE

- Concomitant medications used to treat AEs (a specific list of concomitant medications associated with each risk will be provided)

For each subject and each AE, the worst severity recorded will be attributed and used in the by-severity summaries. Similarly, the worst causality (most related to treatment) will be attributed and used in the by-causality summaries. If causality is missing, the worst case will be assumed (related to treatment).

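### No adverse event table isolates the period after week 10, and the Grade 3+, SAE, AESI and dose-modification tables are not split at week 10, where the two schedules converge.

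*SAP*

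**What the plan says.** SAP 3.1 gives the schedules. "Arm 1: duvelisib 25 mg BID for one 10-week cycle followed by 25 mg BID on Weeks 3 and 4" of each later 4-week cycle; Arm 2 takes drug in Weeks 1, 2, 5, 6, 9 and 10 of Cycle 1 and then follows the same later schedule. Arm 1 therefore has no holiday before Cycle 2, and the arms do not differ in schedule after Cycle 1.

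Protocol 4.2 states the safety question: "will the holidays reduce the frequency, severity, and/or duration of AEs". It adds that in earlier studies most interruptions for toxicity came after 4 cycles.

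SAP 4.11.2 counts as treatment-emergent any event that starts or worsens between first dose and 30 days after last dose. Among its TEAE summaries one is limited in time: "TEAEs occurring during the first 10 weeks of treatment". That bullet names no grade, so reading it as an any-grade table is an inference. These bullets carry no time limit:

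- "Grade 3 or higher TEAEs (all causalities")
- "Treatment-emergent SAEs (all causalities")
- "TEAEs resulting in any dose modification (dose hold, dose reduction and/or discontinuation")

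The same holds for the separate hold, reduction and discontinuation tables.

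For AESIs, SAP 4.11.2.1 says "For each risk, PTs will be summarized at the grouped PT and individual PT", again over the whole window. The one time element is "Time to initial onset (defined as AE start date – first dose date + 1").

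**The concern.** Week 10 separates two different questions. Before it, the randomized arms receive different schedules, so this is where the effect of early holidays on toxicity can be seen directly. After it, both arms are on holidays, so this is where Arm 1's experience under holidays lies. The SAP recognises the boundary but applies it to one table only.

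Two things are at stake. First, for severe, serious and special-interest events, and for events leading to dose changes, the Cycle 1 contrast is shown only after mixing with a long period in which the schedules are identical. A real early difference would look smaller than it was. Second, within Arm 1, events that arose before any holiday are counted together with events that arose under holidays. A reader asking how holiday dosing is tolerated in Arm 1 has no summary table to consult.

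**Working it through.** The plan gives no AE rate or contrast to reproduce. The check has three parts.

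**1. Which summaries are split at week 10** (SAP 4.11.2 and 4.11.2.1)

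| Summary | Weeks 1–10 alone | After week 10 alone |
|---|---|---|
| TEAEs, no grade stated | yes | no |
| Grade 3 or higher TEAEs | no | no |
| SAEs | no | no |
| Hold, reduction, discontinuation | no | no |
| AESI incidence | no | no |

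**2. How fast the schedule contrast fades** (SAP 3.1; full adherence assumed)

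Cycle 1 dosing days: Arm 1, 10 × 7 = 70; Arm 2, 6 × 7 = 42. Each later 4-week cycle adds 14 days in both arms. With k later dosing blocks completed, Arm 1 has 70 + 14k days and Arm 2 has 42 + 14k. By weeks 26, 52 and 104, k is 4, 10 and 23; weeks 51–52 and 103–104 are holiday weeks.

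| To week | Arm 1 days | Arm 2 days | Ratio | Share of Arm 1 days on the holiday schedule |
|---|---|---|---|---|
| 10 | 70 | 42 | 1.67 | 0% |
| 26 | 126 | 98 | 1.29 | 56/126 = 44% |
| 52 | 210 | 182 | 1.15 | 140/210 = 67% |
| 104 | 392 | 364 | 1.08 | 322/392 = 82% |

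**3. Illustration of dilution. All rates are assumed; the documents give none.**

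Assume a constant hazard per dosing day and an Arm 2 Cycle 1 risk p of 5%, 10% or 20%. The risk after d dosing days is 1 − (1 − p)^(d/42). For p = 10%, Arm 1 at week 10 is 1 − 0.9^(70/42) = 16.1%. At week 52, Arm 1 is 1 − 0.9^(210/42) = 41.0% and Arm 2 is 1 − 0.9^(182/42) = 36.7%.

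| Assumed p | Week 10, Arm 1 vs Arm 2 | Risk ratio | Week 52, Arm 1 vs Arm 2 | Risk ratio |
|---|---|---|---|---|
| 5% | 8.2% vs 5.0% | 1.64 | 22.6% vs 19.9% | 1.14 |
| 10% | 16.1% vs 10.0% | 1.61 | 41.0% vs 36.7% | 1.12 |
| 20% | 31.1% vs 20.0% | 1.55 | 67.2% vs 62.0% | 1.08 |

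A second set of assumed rates points the same way. Take Grade 3+ risk in Weeks 1–10 as 20% in Arm 1 and 12% in Arm 2, and a later risk of 35% in both. Treat the two periods as independent, with every subject entering the second. Pooled risk is 1 − 0.80 × 0.65 = 48.0% against 1 − 0.88 × 0.65 = 42.8%, so 8.0 points become 5.2. With a later risk of 20% to 50%, the pooled difference is 6.4 to 4.0 points.

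**The case against.** The strongest case is that the whole-period table is the right main display. Arm 1 is defined as a continuous cycle followed by holidays, so that table describes the assigned schedule. It keeps all treated subjects and captures delayed effects of Cycle 1. No formal comparison between arms is planned (Protocol 9.4.1), and the primary analysis is untouched. All of this stands. It argues for keeping the whole-period tables, not against adding a descriptive split.

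A reader might infer that Arm 1's safety under holidays is never shown. The documents do not support that. SAP 4.11.4 and 4.11.5.1 plan laboratory, blood pressure and heart-rate boxplots at each scheduled visit, SAP 4.11.1 gives relative dose intensity by cycle, and SAP 4.11.2.1 gives AESI time to onset and a listing with onset date, severity, seriousness and action taken. What is missing is an AE summary table.

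A reader might also infer that both arms' tables mix continuous and holiday dosing. Only Arm 1's do; Arm 2 has holidays from Week 3. Nor is the Cycle 1 contrast for TEAEs overall diluted, because the first-10-weeks table shows it.

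Nor is it right that subtraction gives nothing. The overall count for a preferred term minus its 10-week count gives subjects whose first onset came after week 10. Recurrences, grade and a denominator of subjects who continued are lost, and the Grade 3+, SAE, AESI and dose-modification tables have no early counterpart to subtract.

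Protocol 9.4.4 and SAP 4.14 allow further analyses, but commit to none. Finally, a split does not give a clean estimate of safety under holidays: Cycle 2 opens with two weeks off drug, so early events there follow continuous dosing in Arm 1, and later toxicity may reflect Cycle 1 exposure. That limitation is real and should be stated with the tables.

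**Conclusion.** The point holds as a gap in descriptive safety reporting. No TEAE table isolates the time after week 10, and no Grade 3+, SAE, AESI incidence or dose-modification table is split there. For these events the plan cannot show, in summary form, the only weeks in which the schedules differ.

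The direction of the dilution follows from the schedules: the planned-dosing ratio falls from 1.67 to 1.15 by week 52 and to 1.08 by week 104, assuming full adherence and continued treatment. Its size on the AE scale is unknown. The illustrations rest on assumed rates, on a constant hazard per dosing day in one case, and on independent periods with equal later risk in the other.

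The response-rate analysis and its decision rules are unaffected. This is an inexpensive improvement that bears directly on the study's stated safety question.

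**What to change.** Keep the whole-period tables as the main display. Add to SAP 4.11.2 and 4.11.2.1 descriptive versions of the Grade 3 or higher, SAE, AESI and hold, reduction and discontinuation tables, by arm and by period of onset or worsening:

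- **Period (a):** first dose to the day before Cycle 2 Day 1, or to last dose + 30 days for subjects who never start Cycle 2. Denominator: all treated subjects.
- **Period (b):** Cycle 2 Day 1 to last dose + 30 days. Denominator: subjects who started Cycle 2.

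Count a preferred term in each period in which it starts or worsens in grade, in line with the SAP's own definition of treatment emergence. The extension in (a) matters. Without it, a subject who stops in Week 9 and has a Grade 3 event in Week 12 would be in neither table. Because the Cycle 2 Day 1 visit has a ±3-day window (Protocol Table 1), state that the subject's actual date is the cut.

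Footnote the downside: period (b) is a selected subset, no longer the randomized groups, and its events may reflect carry-over from Cycle 1 dosing.

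The cost is a few extra table runs, using event and dosing dates that the SAP already relies on.

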1. PROTOCOL SUMMARY

1.1. Synopsis

Study Title: A Phase 2, randomized, open-label, 2-arm study comparing 2 intermittent dosing schedules of duvelisib in subjects with indolent non-Hodgkin lymphoma (iNHL)

Protocol Number: VS-0145-229

Phase: 2

Rationale: Dosing with duvelisib 25 mg twice daily (BID) has been shown to be efficacious in multiple Phase 1-3 studies including subjects with iNHL. The efficacy, safety and tolerability of this dose supported the US approval of duvelisib for the treatment of adult patients with relapsed or refractory (R/R) chronic lymphocytic leukemia (CLL)/small lymphocytic lymphoma (SLL) after at least 2 prior therapies and accelerated approval in adult patients with R/R follicular lymphoma (FL) after at least 2 prior systemic therapies. The current study will evaluate whether efficacy can be achieved and maintained, with acceptable or improved safety and tolerability, by inclusion of pre specified 2-week drug holidays in 2 different 25 mg BID schedules in subjects with R/R iNHL.

Objectives and Endpoints

Objective	Endpoint (see Section 9.4 for definitions)
Primary	
Evaluate the efficacy of duvelisib administered with prescribed drug holidays in subjects with iNHL	Overall Response Rate (ORR) according to the 2007 revised International Working Group (IWG) Criteria (Cheson 2007)
Secondary	
Evaluate supportive efficacy measures of duvelisib administered with prescribed drug holidays in subjects with iNHL	
ORR according to 2014 Lugano criteria (Cheson 2014) Note: all additional secondary response endpoints as well as progression-free survival (PFS), will be assessed separately using 2007 revised IWG criteria (Cheson 2007) and 2014 Lugano criteria (Cheson 2014)ORR, at 6, 12, 18, and 24 months after first dose of study interventionProgression-free SurvivalTime to Treatment Failure (TTF)Duration of Response (DOR)Overall Survival (OS)Lymph Node Response Rate (LNRR)Time to the First Response (TTFR)

Evaluate the safety and tolerability of duvelisib administered with prescribed drug holidays in subjects with iNHL	Adverse events (AEs), serious AEs (SAEs), vital signs, physical examinations, and clinical laboratory values
Characterize the pharmacokinetics (PK) of duvelisib and metabolite IPI-656 when duvelisib is administered with prescribed drug holidays in subjects with iNHL	PK parameters for duvelisib and metabolite IPI-656
Exploratory	

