Evaluate Quality of Life (QoL) in subjects with iNHL treated with duvelisib with prescribed drug holidays	
 Eastern Cooperative Oncology Group (ECOG) Performance Score EQ-5D-3L questionnaire responses
Evaluate potential biomarkers of clinical efficacy and/or safety of duvelisib administered with prescribed drug holidays in subjects with iNHL	
 Blood assessments of immune cell populations, chemokines, cytokines, phosphorylated proteins, and/or circulating tumor ctDNA Fecal assessments of protein, DNA, and or RNA Tumor biopsy evaluation of biomarkers such as gene and copy number variation, RNA expression, protein expression, and/or immune cell content

Overall Design:
 
This is a Phase 2, randomized, open-label, 2-arm study designed to evaluate the efficacy and safety of prescribed drug holidays of duvelisib treatment in subjects with R/R iNHL who have received at least 1 prior systemic therapy.
 
Subjects will be stratified by number of prior therapies (1 or > 1), bulky disease status (longest diameter of baseline lesion < 5 cm or ≥ 5 cm) and time since last recurrence (≥ 24 months or < 24 months). Subjects will be randomized to Arm 1 or Arm 2 in a 1:1 fashion. Each treatment arm will be analyzed separately.
 
The study is a 2-stage design. For each arm: in the first stage, approximately 15 subjects will be enrolled. Responses will be assessed by the Investigator according to the 2007 revised IWG criteria (Cheson 2007) (primary endpoint) and 2014 Lugano criteria (Cheson 2014). The evaluation of the first stage will take place after the 15 enrolled subjects have been followed for a minimum of 3 cycles. If there are fewer than 6 responders (partial response [PR] or complete response [CR]) among the first 15 subjects in each arm, consideration may be given to stopping the arm. Otherwise, 36 additional subjects will be enrolled for a total of 51 per arm. Enrollment will be continuous between Stage 1 and Stage 2.
	

Number of Subjects:
 
Approximately 102 subjects will be enrolled and randomized at multiple sites globally. The study will employ a 2-stage approach with a planned enrollment of approximately 30 subjects for Stage 1 and up to approximately 72 additional subjects for Stage 2.
	

Intervention Groups and Duration:

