9.1. Statistical Hypotheses

This study will test the null hypothesis that the ORR for each arm is $\leq 30\%$ against the alternative that ORR is $\geq 55\%$.

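### The only TEAE table selected on a between-arm difference can list Arm 1 excesses but never Arm 2 excesses

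*SAP*

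**What the plan says.** SAP 4.11.2 states that "TEAEs will be summarized for each treatment arm by MedDRA SOC and PT", or by one of these levels alone, and then lists the tables. Most are unfiltered. Several carry a frequency threshold, and one carries a difference threshold: TEAEs in at least 5% of subjects that occur at 2% or more "higher incidence in subjects on Arm 1 (all grades, all causalities". No counterpart exists for Arm 2. The next bullet, for Grade 3 or higher events, applies its 5% threshold to the percentage "of subjects on either arm (all causalities".

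The same list includes TEAEs in the first 10 weeks of treatment, with no frequency or direction filter. In SAP 4.11.2.1, "The following risks will be summarized as Adverse Event of Special Interest" introduces further summaries by risk category.

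On response, the protocol title describes a "randomized, open-label, 2-arm study comparing 2 intermittent dosing schedules of duvelisib". Protocol 4.2 asks whether uninterrupted dosing is needed early, or "can comparable tumor responses be achieved starting with alternating 2-week periods of dosing and holidays". The analysis is per arm throughout: the synopsis says "Each treatment arm will be analyzed separately", and protocol 9.1 says "This study will test the null hypothesis that the ORR for each arm is" at most 30%. Protocol 9.4.1 and SAP 4.10.1 both say that no formal between-arm comparison is planned.

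**The concern.** A one-way difference filter is natural when a test arm is set against a control. Here protocol Table 4 classes the use of duvelisib as experimental for both arms. Protocol 4.2 also leaves it open whether holidays reduce the frequency, severity or duration of adverse events. A table that can list only Arm 1 excesses can support the expected answer but cannot show a result that goes against it. A reader who treats it as the summary of where the schedules differ would see one side only.

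The bullet also does not say whose 5% is meant. Neighbouring bullets specify all treated subjects or either arm; this one says only subjects.

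A lesser matter is that the response question in protocol 4.2 is comparative, while the planned ORR output is two separate estimates with exact intervals and no interval for the gap.

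**Working it through.** **The plan's own figure.** The stated design is 15 then 51 subjects per arm, continuing with at least 6 responders and succeeding with at least 22, with one-sided error 0.025 and power 90% (SAP 4.13). Treating the stage 1 rule as binding, sum over x = 6 to 15 of P(X1 = x) × P(X2 ≥ 22 − x), with X1 ~ Bin(15, p) and X2 ~ Bin(36, p). This gives 0.0246 at p = 0.30 and 0.9035 at p = 0.55. The design reproduces, and nothing below touches it.

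**TEAE rule: inputs.**
- 51 per arm (SAP 4.13).
- Thresholds of 5% and 2% (SAP 4.11.2), with the 2% read as percentage points.
- True event rates are assumptions; the documents give none by schedule.
- The 5% floor is read as met in either arm, and alternatives are checked below.

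One subject is 1/51 = 1.96%, just under 2%, so listing needs a gap of two subjects (2/51 = 3.92%). With 50 per arm, one subject is exactly 2.0% and would suffice.

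With independent X1 ~ Bin(51, p1) for Arm 1 and X2 ~ Bin(51, p2) for Arm 2, sum the joint probabilities over outcomes that meet the floor and
- one-way: (X1 − X2)/51 ≥ 0.02
- two-way: |X1 − X2|/51 ≥ 0.02

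| True rate Arm 1 | True rate Arm 2 | One-way (current) | Two-way |
|---|---|---|---|
| 10% | 20% | 0.031 | 0.876 |
| 20% | 10% | 0.844 | 0.876 |
| 20% | 20% | 0.355 | 0.710 |
| 10% | 10% | 0.308 | 0.616 |

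The first row is the asymmetry. The 0.031 consists entirely of samples in which Arm 1 comes out higher by chance. The last two rows are the price of symmetry: with no true difference, listings double.

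**Sensitivity to the floor, 10% v 20%.** The one-way figure is 0.031 whether the 5% is read as either arm, pooled or Arm 1 only. The two-way figure is 0.876, 0.875 and 0.772 respectively.

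**Where Arm 2 remains visible.** The schedules differ only in weeks 1 to 10: 10 × 7 = 70 dosing days on Arm 1 and 6 × 7 = 42 on Arm 2. From Cycle 2 they are the same (SAP 3.1). The table for the first 10 weeks covers that period, by arm and without a filter.

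**ORR difference, Arm 2 minus Arm 1.** The Newcombe interval combines the Wilson limits (l, u) of each arm:
- lower = d − √[(p2 − l2)² + (u1 − p1)²]
- upper = d + √[(u2 − p2)² + (p1 − l1)²]

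Wilson limits are 41.4% to 67.7% for 28/51 (54.9%) and 30.5% to 56.7% for 22/51 (43.1%).
- 28/51 in both arms: d = 0, interval −18.6 to +18.6 points.
- 22/51 on Arm 2 and 28/51 on Arm 1: d = −11.8, interval −29.8 to +7.4 points.

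These widths hold only if both arms reach 51. If the rule of fewer than 6 responders in 15 were followed, an arm would stop with probability 0.08 at a true ORR of 55% and 0.72 at 30%.

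**The case against.** The one-way filter has a plausible basis. Arm 1 has more dosing in the first 10 weeks, and protocol 4.2 words the tolerability question as whether holidays reduce adverse events, so an Arm 1 excess is the expected direction. That may explain the bullet. It does not justify excluding the opposite result, and the SAP does not offer it as a reason.

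A two-way rule is also a weak filter: it would list about 7 in 10 terms with a true 20% rate in both arms. This stands, and is why the table needs a descriptive label.

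Three stronger readings are tempting and not supported:
- That Arm 2 toxicity is concealed. The unfiltered by-arm tables, the special-interest summaries and the first-10-weeks table all show Arm 2.
- That this table is the plan's instrument for comparing tolerability. The SAP assigns it no such purpose.
- That the title commits the trial to a response comparison that the analysis then omits. The title says only that two schedules are compared. The question about comparable responses appears in the rationale in protocol 4.2, no listed objective or endpoint is a between-arm contrast, and the per-arm plan is open and consistent.

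On ORR, a reader can derive the difference from the per-arm counts, and SAP 4.14 permits added analyses under a separate plan. Nor can one claim that specifying it in advance would precede all knowledge of results: the trial is open-label, and SAP version 2.1 followed a dry run whose content is not described. These points reduce the ORR item to an option.

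**Conclusion.** The point holds for the TEAE table and is minor. The single difference-selected table is one-directional between two experimental schedules. Under the assumed 10% v 20% it would list an Arm 2 excess with probability 0.03, against 0.84 for the mirror-image Arm 1 excess. These figures rest on assumed event rates, 51 treated subjects per arm and independence between arms; the 0.03 does not depend on how the 5% floor is read. The harm is to emphasis, since no event, listing, primary test or error rate is affected.

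The missing ORR difference is not an error. At full size the interval would be about 19 points either side when both arms have 28/51, too wide to show that responses are comparable. Its only use would be to discourage over-reading of two similar rates.

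**What to change.** **Recommended.** Reword the SAP 4.11.2 bullet along these lines: TEAEs whose incidence reaches 5% in at least one arm and differs between arms by 2 percentage points or more, in either direction. Show which arm is higher and label the table descriptive. This makes two changes, and both should be recorded: the rule becomes symmetric, and the denominator of the 5% floor is settled. The cost is one bullet and one table specification, plus the doubling of chance listings shown above. No new data are needed.

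**Optional.** Add one row with the unadjusted ORR difference, Arm 2 minus Arm 1, with a Newcombe 95% interval and no p-value. Unadjusted agrees with SAP 4.10.1.2, and a descriptive estimate does not conflict with the statement that no formal comparisons are planned. Use the actual arm sizes and do not print a fixed width, because an arm may stop at about 15 subjects. State beside it that the interval cannot support equivalence or non-inferiority. The per-arm tests against 30% stay primary, and the sample size does not change.
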